This study design incorporates a matched cohort design placed in a non-concurrent prospective setting (incorporating mortality, morbidity, and follow-up studies). Detailed computer searches of Air Force personnel records, with several cross-referencing techniques, will ensure total ascertainment of the RANCH HAND population. Since there was a documented higher concentration of TCDD contamination prior to 1965, this factor will be incorporated in the development of an exposure index. A group of C-130 crewmembers and support personnel will form the control group. They will be matched to RANCH HAND personnel for the variables of age, AFSC, length of time in Vietnam, and race. The ten best matches for each exposed subject will form a control set and they will be randomly ordered. In the analysis of mortality, each exposed subject and a 50% random selection from each control set will be followed yearly. The first of the randomized mortality controls will be selected and entered into the questionnaire and physical examination phases of the study. If this primary control drops out, for reasons other than death, the next control will be selected from the control set so that both statistical power and loss to study bias in the follow-up

study may be improved. All RANCH HAND personnel and their primary controls will be asked to complete a telephone questionnaire and will be offered a comprehensive physical examination, with special emphasis being placed on dermatologic, neuropsychiatric, hepatic, reproductive and neoplastic conditions. An adaptive physical examination and questionnaire will be developed to be used in years three and five of the follow-up study, which is set for a minimum of five years duration. The unusual capabilities of the USAF in the collection, storage, and retrieval of data will allow integration of the various data collection methods used throughout the study. Expected biases and study difficulties include differences in group accountability, risk taking behavior bias in the volunteer RANCH HAND group, response bias, interviewer bias, loss to study difficulties, and variability of procedures performed, as well as the political overlay of this effort.

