Operation RANCH HAND personnel flew C-123 aircraft in RVN during 1962-1970. Data from hand-compiled lists obtained through the RANCH HAND Association (a reunion organization), Air Force personnel computer entries, historical records and actual C-123 flight orders, place the estimated study population at approximately 1200 individuals. Of those personnel confirmed by the USAF computer system, 25% are still on active duty, with the remainder being composed of retired or separated persons. An indepth search to identify all RANCH HAND participants is being conducted of all organizational records stored at the Military Records Division, National Personnel Records Center (NPRC), St. Louis, Missouri. Detailed advertisements in active/retired military trade journals, VA publications, and local newspapers may be pursued in the near future to insure maximal ascertainment/identification of the exposed group. Introductory letters will be sent to the last known address of all identified persons, and nonresponse will be pursued by cross-locator systems available within the government (e.g., Social Security Administration, VA, Internal Revenue Service). Significant efforts will be made to account for at least 99% of the total population (see Figure A-2, Section XII). Because of the limited number of estimated RANCH HAND personnel (1200), no subsampling of the exposed group is planned in any phase of the study. All members will be strongly encouraged to participate in all phases of the investigation.

(a) Known or Predicted Characteristics of the Exposed Group

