All exposed aircrew personnel are males currently ranging in age from approximately 28-58 years. The normal C-123 crew composition was one pilot and one copilot/navigator (both officers) and one spray equipment console operator in the rear of the aircraft (enlisted); thus, the aircrew officer-enlisted ratio will be approximately 2:1. The inclusion of RANCH HAND support personnel (predominantly enlisted) in the study will make the overall officer-enlisted ratio approximately 1:2. While almost all officers were Caucasian, approximately 10-14% of the enlisted men were Black. Attempts will be made to identify all maintenance personnel assigned to the RANCH HAND units. Maintenance of the RANCH HAND aircraft was performed within a step-wise organizational structure. Routine daily maintenance (primary) was conducted by flight line support personnel who were often dedicated exclusively to RANCH HAND operations. More extensive maintenance (secondary) was carried out by consolidated support units at the base level, which were also responsible for non-RANCH HAND C-123s as well. Major aircraft overhauls and modification were conducted by maintenance units at Clark Air Base, Philippines. The maintenance personnel in these centralized units were not directly assigned to RANCH HAND, and their exposures to RANCH HAND C-123 aircraft and herbicide

cannot be validated. From 1962 through 1964, the primary flight line maintenance teams were dedicated to RANCH HAND aircraft and these individuals can be identified by the mechanisms described above. In 1965, flight line maintenance was performed by personnel of the centralized maintenance organization (secondary) and it may not be feasible to adequately identify these individuals from available records. After 1966, the RANCH HAND organization transferred their base of operations to a new location, and primary maintenance was once again performed by personnel assigned specifically to RANCH HAND. These individuals can again be readily identified. Thus, maintenance personnel directly assigned to RANCH HAND will be included in the study. These complexities are summarized in Table 5.

Table 5

FEASIBILITY OF IDENTIFYING AIRCRAFT MAINTENANCE
PERSONNEL (TOTAL POPULATION) EXPOSED TO HERBICIDE ORANGE

Time	Primary Maint Personnel¹	Secondary Maint Personnel²
Jan 1962-Jul 1964	Yes	No
Aug 1964-Dec 1966	Yes/No ³	No
Jan 1967-Apr 1970	Yes	No

¹individual assigned to RH; denominator known

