A review of all specialized flight units present during the RVN conflict, reveals clearly that there is no absolutely ideal control group for the RANCH HAND population. C-130 aircrew members and support personnel were selected because of sufficient population size, similar training profiles, and psychologic similarities to the RANCH HAND Group.

Total ascertainment of the C-130 population is being conducted by computer selection for specific military flying organizations, foreign country service and years of service. Over 2.3 million personnel records have already been scanned and the approximate C-130 sample size is 25,000 individuals. Aircrew members who flew C-130 aircraft in RVN during 1962-1970 will be selected as controls for the RANCH HAND aircrew population and the C-130 flight line maintenance population will be ascertained from personnel records by similar mechanisms, and will serve as the specific control population for the RANCH HAND support personnel. The proportions on active duty, and non-active duty status are expected to parallel the patterns in the exposed group.

Another possible control group, the non-RANCH HAND C-123 population, is known to be too small (approximately 3000) to provide adequate sampling flexibility and replacement under the proposed matched variable concept (see below and Section VI, I). Many of the RANCH HAND aircraft were reconfigured for transport and insecticide missions and thus, non-RANCH HAND crews responsible for these other missions, may have been exposed to significant Herbicide Orange residues in these aircraft.

Therefore, this group may not have been truly unexposed to herbicides, and was discarded as an appropriate control population. Crewmembers of C-7 transport aircraft were also considered as a potential control group; however, because of small size (1000-1200) and the fact that they served in RVN only during the post 1967 era, they were also dropped from consideration.

(a) Known or Predicted Characteristics of the Control Group

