The normal crew composition of a C-130 is three officers and two enlisted personnel. The control group will be "pure" from the standpoint of lack of occupational exposure to herbicide. The entire control group will be considered "nonvolunteer" with respect to abnormally high combat risk. While in general they will possess lifestyle characteristics and socio-economic backgrounds similar to the exposed group, their overall combat morbidity/mortality and the resultant stress influences upon general health may be slightly less than in the exposed group. For those separated and retired C-130 controls, similar proportions to the exposed group are expected to be employed in the aerospace industry. Known and estimated factors of the control and exposed populations are summarized in Table 6.

(4) Matching Procedures and Rationale

Each member of the exposed group will be computer matched to a set of C-130 controls comprised of at least 10 individuals using four variables. Since the two groups are highly selected and inherently similar with respect to many variables, very close matches are feasible. This epidemiologic design incorporates a matched concept because: (1) a matched cohort design will provide maximum test power throughout the entire study, (2) statistical intergroup comparisons may be made without normalization by four key variables known to effect symptom frequencies of interest, thus providing greater power for complex statistical testing, and (3) close matching is feasible and necessary for some of the anticipated analyses of the physical examination findings. Matches will not necessarily be rigidly maintained throughout the analytic phase, depending upon the particular analysis. It is apparent that following the match, both exposed and control populations will be very nearly identical with respect to the four influencing variables so that a replacement concept is feasible (see E below). In the event that frequent match breaks still occur, stratification techniques can be used.

Matching will be conducted for (1) age, by year of birth, and closest month possible, (2) Air Force Speciality Code (AFSC) as an absolute match, (3) length of time spent in Vietnam, to the closest six month period, and (4) race (Caucasian versus non-Caucasian) as an absolute match. These variables are listed in priority order of the match sequence. Specific rationale for these

Table 6

COMPARISON OF THE STUDY GROUP TO POSSIBLE CONTROL GROUPS BY
KNOWN AND ESTIMATED FACTORS

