Given a specific scenario, for example, a 25 sq ft spill involving two gallons of Herbicide Orange on the aircraft floor during a mission, the model could determine the magnitude and duration of the chemical concentration in the areas near the console operator versus the air concentration in the cockpit. The key to determining the magnitude and route of exposure of C-123 aircrew members is obviously selecting the most likely aircraft configuration used during RANCH HAND and determining the frequency and magnitude of spills within the aircraft. These observations will come from the recollection of personal observations by RANCH HAND personnel.

The 355th TAS/Spray Branch, Rickenbacker AFB OH is presently using the C-123 aircraft configured with the A/A 45 Y-1 Internal Dispenser. Air flow measurements, volume determinations, and surface temperature data will be obtained for modeling and simulant studies. A suitable Herbicide Orange Simulant was developed by the USAF in 1965 and consisted of glycerine, water, and sodium thio-sulfate in a ratio of 68:16.8:15.2, respectively. Since physical and chemical data are available on the simulant, the addition of a sodium fluorescein tracer may permit particulate sizing and quantitative determinations of the extent of contamination in the air of the aircraft and on the surfaces of the aircraft and on aircrew members.

An estimate of relative exposure for non-flying personnel will be developed in a different manner. The Air Force conducted extensive industrial hygiene monitoring programs during the dedrumming and incineration of Herbicide Orange, Project PACER HO, (See Young, et al., 1978). These monitoring data (e.g., breathing zone data) and recently conducted, but as yet unpublished data on percutaneous absorption of 2,4,5-T in humans during actual spray operations in reforestation programs (Dow Chemical U.S.A., Midland MI, 1979), will permit more refined calculations of exposure estimates for this group of individuals. When these concepts are used to calculate an exposure estimate, there will be a group of RANCH HAND individuals with an exposure index of zero (clerical/administrative personnel with little or no flight line duties).

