In the event that these more elaborate exposure index calculations are not feasible, two other approaches to the exposure estimate are available. A crude index can be constructed, based solely on the duration of RVN duty and the TCDD concentration of the herbicides used each year. While such an index would be less precise in defining an individual's estimated level of exposure, it would still permit valid comparisons within the RANCH HAND population. Stratification techniques could also be employed using AFSC and duration of exposure (RVN duty) as the grouping criteria.

VI. Statistical Methodology

A. Introduction

The design of the study is presented in schematic form in Figure 6. R' refers to the RANCH HAND personnel and C'' refers to the collection of all possible control individuals. As defined, R' and C'' will contain individuals who are deceased. Since C'' may be 15 to 25 times larger than R', a randomized subsample C' of C'' will be obtained. C' will be constructed from C'' by computer selection of the ten best matched controls for each exposed study subject. As previously noted, close matches will be made for the variables of age, AFSC, RVN tour length, and race. The matched controls will form ten cohorts, C₁ through C₁₀, as previously shown in Figure 1. A 50% random sample from each of the matched control sets of 10 will be selected for inclusion in the mortality assessment so that a group, C' is obtained that consists of 5 matched controls for each exposed subject. These controls will be designated as initial replacement candidates for the morbidity and followup studies. The remaining individuals in the control set will be additional replacement candidates in the event that replacement must occur beyond the members of the mortality set (see Figure 2). C' will be constructed without regard to whether the individual is currently living or dead so that an assessment of mortality can be accomplished.

Referring again to Figure 6, R and C indicate living RANCH HAND members and primary matched controls. If $m_{R'}$ is the proportion of R' found to be deceased, then,

$$R = (1 - m_{R'})R'$$

The questionnaire will provide data concerning specific symptoms and other findings in the R and C groups. Thus, various questionnaire finding rates in R, s_R , will be calculated and compared with the corresponding rates in C, s_C .

[figure not shown]

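### Clerical and administrative RANCH HAND men expected to score zero exposure are counted as exposed in the central group comparisons, and the text conflicts on their controls and exposure class

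*Protocol*

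**What the plan says.** **Exposure.** Section V.G(2) states that "there will be a group of RANCH HAND individuals with an exposure index of zero (clerical/administrative personnel with little or no flight line duties". Section V.G(1) sorts most men into three exposure classes. It puts support personnel other than crew chiefs and mechanics in the middle class and has no zero class.

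**Cohort.** Section V.B(1) says that "no subsampling of the exposed group is planned in any phase of the study". It also counts support staff as members: "The inclusion of RANCH HAND support personnel (predominantly enlisted) in the study will make the overall officer-enlisted ratio approximately 1:2". Section VI.A defines the exposed group R' as the RANCH HAND personnel, without exception.

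**Controls.** The Executive Summary says "A group of C-130 crewmembers and support personnel will form the control group", and Section V.B(3) opens in the same broad terms. Section V.B(3) then becomes narrower: "the C-130 flight line maintenance population will be ascertained from personnel records by similar mechanisms, and will serve as the specific control population" for RANCH HAND support personnel. Section V.B(4) takes "Air Force Speciality Code (AFSC) as an absolute match".

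**Analysis.** Section VI.A treats the exposed-to-control ratios of mortality, symptom and finding rates as central to defining a herbicide effect. Section VI.C supports McNemar's test with exposure coded 0/1. Sections V.F and VI.H add regression on an exposure index. If the full index cannot be built, Section V.G(2) offers two fallbacks. One is "A crude index can be constructed, based solely on the duration of RVN duty and the TCDD concentration" of the herbicides used each year. The other is stratification by AFSC and duration.

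**The concern.** The stated purpose is to find health effects attributable to occupational herbicide exposure. Men whom the protocol itself expects to be unexposed carry the control-level risk. Counting them as exposed shrinks any true difference in the group comparisons, in a study that describes its own power as limited.

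Two further problems concern the same men:

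- **Controls.** AFSC matching is meant to hold education, socio-economic status and crew status constant. If a clerk's control came from flight line maintenance, the pair would differ on what the match is meant to control.
- **Fallback index.** An index without a job term gives a clerk the same score as a console operator with the same tour. That blurs the dose-response analysis that would otherwise separate them.

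**Working it through.** **Inputs.** Table 12, r = 0 row: control rate p2 = .05, exposed rate p1 = .10 (RR 2), alpha .05, stated power .61, .75 and .85 at 250, 350 and 450 pairs. The share z of zero-exposure men is not in the protocol, so z = 5%, 10% and 20% are assumptions.

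**Step 1: reproduce the stated power.** The protocol gives neither the formula nor the sidedness. A two-proportion normal approximation with pooled null variance, one-sided alpha .05 and continuity correction fits this row:

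power = Φ{[(p1 − p2 − 1/n) − 1.645·√(2p̄(1 − p̄)/n)] / √([p1(1 − p1) + p2(1 − p2)]/n)}, with p̄ = (p1 + p2)/2.

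At n = 450: difference .05 − 1/450 = .04778; null SE .01756; alternative SE .01748; (.04778 − 1.645 × .01756)/.01748 = 1.08; power .860.

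| Pairs | Table 12 | Recomputed |
|---|---|---|
| 250 | .61 | .621 |
| 350 | .75 | .766 |
| 450 | .85 | .860 |

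All three agree within 2 points. The same formula does not fit every row: for .20 versus .10 it gives .994 at 450 pairs against a stated .97. It is used here only as a baseline for this row.

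**Step 2: dilution.** If a share z of the exposed group has the control rate, the group's rate is p1* = (1 − z)·p1 + z·p2, so observed RR = 1 + (RR − 1)(1 − z).

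- z = 5%: p1* = .0975, RR 1.95
- z = 10%: p1* = .0950, RR 1.90
- z = 20%: p1* = .0900, RR 1.80

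A true RR of 3 becomes 2.9, 2.8 and 2.6.

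**Step 3: keep the men or remove their pairs.** Keeping them uses p1* at 450 pairs. Removing them restores p1 = .10 with 450(1 − z) pairs.

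| z | RR if kept | Power if kept (450 pairs) | Pairs if removed | Power if removed |
|---|---|---|---|---|
| 0 | 2.00 | .860 | 450 | .860 |
| 5% | 1.95 | .831 | 428 | .843 |
| 10% | 1.90 | .798 | 405 | .823 |
| 20% | 1.80 | .718 | 360 | .778 |

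A two-sided test without continuity correction starts lower, at .814, and shows the same pattern: .779, .741 and .653 if kept; .794, .772 and .722 if removed.

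**Step 4: set the text side by side.**

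- *Control pool.* The Executive Summary and the opening of Section V.B(3) allow C-130 support personnel in general. The operative sentence in Section V.B(3) names flight line maintenance only, while Section V.B(4) demands an exact AFSC. On the narrow wording, no pool is named for an administrative AFSC.
- *Exposure class.* Section V.G(1) puts other support personnel in the middle class. Section V.G(2) scores the clerical men zero.
- *Fallback.* The full index in Section V.G has a crew position/AFSC term. The crude index does not.

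**The case against.** The strongest reply is that the protocol already looks beyond group membership. Section VI.H allows the exposure variable to be graded, and under a graded variable a zero-index clerk is not coded as exposed. Sections V.F and VI.H plan regression on the index, and the second fallback in Section V.G(2), stratification by AFSC, would separate clerks from console operators. This stands in part. It rules out the reading that every comparison treats these men as exposed. It does not mend the rate ratios or the 0/1 contrast: the regression comes on top of those, the index is only to be attempted, and the AFSC strata are optional.

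A reader might also infer that these men have no possible control and must be mismatched or dropped. The document does not support that. The broader support-personnel wording appears twice, and no list of the AFSCs in the C-130 pool is given. What is shown is a conflict to reconcile.

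Keeping the whole unit can also be defended. The zero group is described as having little or no flight line duty, work schedules were seldom routine, and AFSC alone may misclassify some men. This argues against making the restricted comparison the only primary one. It does not argue against showing it.

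Finally, the gain in power from exclusion is small: about 1 point at an assumed 5% and 2 to 3 points at 10%. That is correct. The stronger reason for the restricted analysis is that it removes the bias in the estimate.

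**Conclusion.** The concern holds in this form: the central exposed-versus-control comparisons include men whom the protocol expects to be unexposed, so they are biased toward no effect, and the planned index regression does not correct them. The bias is slight if the group is a few percent. For a true RR of 2, it brings power below .80 from a share of about 10%, taking the calculation that matches Table 12 for that row. The size rests on an assumed share, on truly zero exposure in these men, and on their having the control rate of disease. The conflicts over control pool and exposure class, and the missing job term in the crude index, can be read directly from the text and need no assumption.

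**What to change.** 1. Before any outcome is seen, flag clerical and administrative men without flight line duty, using AFSC confirmed by personnel records, and report their number.
2. Prespecify each main exposed-versus-control comparison twice: with all members, and with the flagged men and their controls removed.
3. Use the flagged men as the zero-dose reference in the exposure regression.
4. State that their controls come from administrative AFSCs in C-130 units, so that the absolute match holds.
5. Add an AFSC/job term, zero for these men, to the crude fallback index.
6. Reconcile the Executive Summary and Sections V.B(3), V.B(4), V.G(1) and V.G(2) on their control pool and exposure class.

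The cost is protocol wording, a filter on records already being searched, and a wider AFSC list in the C-130 computer selection. The restricted analysis has somewhat fewer pairs, and AFSC may misclassify a few men who had some flight line duty. Showing both analyses limits the harm from either.
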